5. PHARMACOLOGICAL PROPERTIES

5.1 Pharmacodynamic properties

Pharmacotherapeutic group: Posterior pituitary lobe hormones ATC code: H01B B02

Mechanism of action

Oxytocin is a cyclic nonapeptide that is obtained by chemical synthesis. This synthetic form is identical to the natural hormone that is stored in the posterior pituitary and released into the systemic circulation in response to suckling and labour.

Oxytocin stimulates the smooth muscle of the uterus, more powerfully towards the end of pregnancy, during labour, and immediately postpartum. At these times, the oxytocin receptors in the myometrium are increased.

The oxytocin receptors are G-proteins coupled receptors. Activation of receptor by oxytocin triggers release of calcium from intracellular stores and thus leads to myometrial contraction.

Oxytocin elicits rhythmic contractions in upper segment of uterus, similar in frequency, force and duration to those observed during labour.

Being synthetic, oxytocin in Syntocinon does not contain vasopressin, but even in its pure form oxytocin possesses some weak intrinsic vasopressin-like antidiuretic activity.

Based on in vitro studies, prolonged exposure of oxytocin had been reported to cause desensitisation of oxytocin receptors probably due to down-regulation of oxytocin-binding sites, destabilisation of oxytocin receptors mRNA and internalisation of oxytocin receptors.

Plasma levels and onset/duration of effect

Intravenous infusion. When Syntocinon is given by continuous i.v. infusion at doses appropriate for induction or enhancement of labour, the uterine response sets in gradually and usually reaches a steady state within 20 to 40 minutes. The corresponding plasma levels of oxytocin are comparable to those measured during spontaneous first-stage labour. For example, oxytocin plasma levels in 10 pregnant women at term receiving a 4 milliunits per minute intravenous infusion were 2 to 5 microunits/mL. Upon discontinuation of the infusion, or following a substantial reduction in the infusion rate, e.g. in the event of overstimulation, uterine activity declines rapidly but may continue at an adequate lower level.

5.2 Pharmacokinetic properties

Absorption

Plasma levels of oxytocin following intravenous infusion at 4 milliunits per minute in pregnant women at term were 2 to 5 microunits/mL.

Distribution

The steady-state volume of distribution determined in 6 healthy men after i.v. injection is 12.2 L or 0.17 L/kg. Plasma protein binding is negligible for oxytocin. It crosses the placenta in both directions. Oxytocin may be found in small quantities in mother's breast milk.

Biotransformation/Metabolism

Oxytocinase is a glycoprotein aminopeptidase that is produced during pregnancy and appears in the plasma. It is capable of degrading oxytocin. It is produced from both the mother and the foetus. Liver and kidney plays a major role in metabolising and clearing oxytocin from the plasma. Thus, liver, kidney and systemic circulation contribute to the biotransformation of oxytocin.

Elimination

Plasma half-life of oxytocin ranges from 3 to 20 min. The metabolites are excreted in urine

whereas less than 1% of the oxytocin is excreted unchanged in urine. The metabolic clearance rate amounts to 20 mL/kg/ min in the pregnant woman.

Renal impairment

No studies have been performed in renally impaired patients. However, considering the excretion of oxytocin and its reduced urinary excretion because of anti-diuretic properties, the possible accumulation of oxytocin can result in prolonged action.

Hepatic impairment

No studies have been performed in hepatically impaired patients. Pharmacokinetic alteration in patients with impaired hepatic function is unlikely since metabolising enzyme, oxytocinase, is not confined to liver alone and the oxytocinase levels in placenta during the term has significantly increased. Therefore, biotransformation of oxytocin in impaired hepatic function may not result in substantial changes in metabolic clearance of oxytocin.

5.3 Preclinical safety data

Pre-clinical data for oxytocin reveal no special hazard for humans based on conventional studies of single dose acute toxicity, genotoxicity, and mutagenicity.

6. PHARMACEUTICAL PARTICULARS

6.1 List of excipients

Sodium acetate tri-hydrate, acetic acid, chlorobutanol, ethanol and water for injections.

6.2 Incompatibilities

Syntocinon should not be infused via the same apparatus as blood or plasma, because the peptide linkages are rapidly inactivated by oxytocin-inactivating enzymes. Syntocinon is incompatible with solutions containing sodium metabisulphite as a stabiliser.

6.3 Shelf life

Five years

6.4 Special precautions for storage

Store between 2°C and 8°C. May be stored up to 30°C for 3 months, but must then be discarded.

6.5 Nature and contents of container

Clear glass 1 ml ampoules. Boxes of 5 ampoules.

6.6 Special precautions for disposal and other handling

Snap ampoules: no file required.

Syntocinon is compatible with the following infusion fluids, but due attention should be paid to the advisability of using electrolyte fluids in individual patients: sodium/potassium chloride (103mmol Na⁺ and 51mmol K⁺), sodium bicarbonate 1.39%, sodium chloride 0.9%, sodium lactate 1.72%, dextrose 5%, laevulose 20%, macrodex 6%, rheomacrodex 10%, Ringer's solution.

7. MARKETING AUTHORISATION HOLDER

Novartis Pharmaceuticals UK Ltd [name]

8. MARKETING AUTHORISATION NUMBER(S)

PL 00101/0959

9. DATE OF FIRST AUTHORISATION/RENEWAL OF THE AUTHORISATION

Date of First Authorisation:03 October 1977Date of Last Renewal:04 October 2002

10. DATE OF REVISION OF THE TEXT

18th February 2016

21.2 Appendix Two: SPC: Syntocinon 10 IU/ml Concentrate for solution for infusion

Summary of Product Characteristics

Syntocinon 10 IU/ml Concentrate for solution for infusion

1. NAME OF THE MEDICINAL PRODUCT

Syntocinon[®] 10 IU/ml Concentrate for solution for infusion

2. QUALITATIVE AND QUANTITATIVE COMPOSITION

Oxytocin.

Concentrate for solution for infusion (in 1mL ampoule) containing 10 IU/mL

Excipient(s) with known effect: Ethanol 5.000mg

For the full list of excipients, see section 6.1.

3. PHARMACEUTICAL FORM

Concentrate for solution for infusion.

A clear, colourless, sterile solution in 1ml clear glass ampoules.

4. CLINICAL PARTICULARS

4.1 Therapeutic indications

Antepartum

- Induction of labour for medical reasons, e.g. in cases of post-term gestation, premature rupture of the membranes, pregnancy-induced hypertension (pre-eclampsia)
- Stimulation of labour in hypotonic uterine inertia
- Early stages of pregnancy as adjunctive therapy for the management of incomplete, inevitable, or missed abortion.

Postpartum

- During caesarean section, but following delivery of the child
- Prevention and treatment of postpartum uterine atony and haemorrhage

4.2 Posology and method of administration

Induction or enhancement of labour: Oxytocin should not be started for 6 hours following administration of vaginal prostaglandins. Syntocinon should be administered as an intravenous

(i.v.) drip infusion or, preferably, by means of a variable-speed infusion pump. For drip infusion it is recommended that 5 IU of Syntocinon be added to 500ml of a physiological electrolyte solution (such as sodium chloride 0.9%). For patients in whom infusion of sodium chloride must be avoided, 5% dextrose solution may be used as the diluent (see Section 4.4 "Special warnings and precautions for use"). To ensure even mixing, the bottle or bag must be turned upside down several times before use.

The initial infusion rate should be set at 1 to 4 milliunits/minute (2 to 8 drops/minute). It may be gradually increased at intervals not shorter than 20 minutes and increments of not more than 1-2 milliunits/minute, until a contraction pattern similar to that of normal labour is established. In pregnancy near term this can often be achieved with an infusion of less than 10 milliunits/minute (20 drops/minute), and the recommended maximum rate is 20 milliunits/minute (40 drops/minute). In the unusual event that higher rates are required, as may occur in the management of foetal death *in utero* or for induction of labour at an earlier stage of pregnancy, when the uterus is less sensitive to oxytocin, it is advisable to use a more concentrated Syntocinon solution, e.g., 10 IU in 500ml.

When using a motor-driven infusion pump which delivers smaller volumes than those given by drip infusion, the concentration suitable for infusion within the recommended dosage range must be calculated according to the specifications of the pump.

The frequency, strength, and duration of contractions as well as the foetal heart rate must be carefully monitored throughout the infusion. Once an adequate level of uterine activity is attained, aiming for 3 to 4 contractions every 10 minutes, the infusion rate can often be reduced. In the event of uterine hyperactivity and/or foetal distress, the infusion must be discontinued immediately.

If, in women who are at term or near term, regular contractions are not established after the infusion of a total amount of 5 IU, it is recommended that the attempt to induce labour be ceased; it may be repeated on the following day, starting again from a rate of 1 to 4 milliunits/minute (see Section 4.3 "Contra-indications").

Incomplete, inevitable, or missed abortion: 5 IU by i.v. infusion (5 IU diluted in physiological electrolyte solution and administered as an i.v. drip infusion or, preferably, by means of a variable-speed infusion pump over 5 minutes), if necessary followed by i.v. infusion at a rate of 20 to 40 milliunits/minute.

Caesarean section: 5 IU by i.v. infusion (5 IU diluted in physiological electrolyte solution and administered as an i.v. drip infusion or, preferably, by means of a variable-speed infusion pump over 5 minutes) immediately after delivery.

Prevention of postpartum uterine haemorrhage: The usual dose is 5 IU by i.v. infusion (5 IU diluted in physiological electrolyte solution and administered as an i.v. drip infusion or, preferably, by means of a variable-speed infusion pump over 5 minutes) after delivery of the placenta. In women given Syntocinon for induction or enhancement of labour, the infusion should be continued at an increased rate during the third stage of labour and for the next few hours thereafter.

Treatment of postpartum uterine haemorrhage: 5 IU by i.v. infusion (5 IU diluted in physiological electrolyte solution and administered as an i.v. drip infusion or, preferably, by means of a variable-speed infusion pump over 5 minutes), followed in severe cases by i.v. infusion of a solution containing 5 to 20 IU of oxytocin in 500ml of an electrolyte-containing diluent, run at the rate necessary to control uterine atony.

Route of administration: Intravenous infusion.

Special populations

Renal impairment

No studies have been performed in renally impaired patients.

Hepatic impairment

No studies have been performed in hepatically impaired patients.

Paediatric population

No studies have been performed in paediatric patients.

Elderly population

No studies have been performed in elderly patients (65 years old and over).

4.3 Contraindications

- Hypersensitivity to the active substance or to any of the excipients listed in section 6.1
- Hypertonic uterine contractions, mechanical obstruction to delivery, foetal distress.

Any condition in which, for foetal or maternal reasons, spontaneous labour is inadvisable and/or vaginal delivery is contra-indicated: e.g.:

- Significant cephalopelvic disproportion
- Foetal malpresentation
- Placenta praevia and vasa praevia
- Placental abruption
- Cord presentation or prolapse
- Overdistension or impaired resistance of the uterus to rupture as in multiple pregnancy
- Polyhydramnios
- Grand multiparity
- In the presence of a uterine scar resulting from major surgery including classical caesarean section.

Syntocinon should not be used for prolonged periods in patients with oxytocin-resistant uterine inertia, severe pre-eclamptic toxaemia or severe cardiovascular disorders.

Syntocinon must not be administered within 6 hours after vaginal prostaglandins have been given (see section 4.5 Interaction with other medicinal products and other forms of interaction).

4.4 Special warnings and precautions for use

Syntocinon must only be administered as an i.v. infusion and never by i.v. bolus injection as it may cause an acute short-lasting hypotension accompanied with flushing and reflex tachycardia.

Induction of labour

The induction of labour by means of oxytocin should be attempted only when strictly indicated for medical reasons. Administration should only be under hospital conditions and qualified medical supervision.

Cardiovascular disorders

Syntocinon should be used with caution in patients who have a pre-disposition to myocardial ischaemia due to pre-existing cardiovascular disease (such as hypertrophic cardiomyopathy,

valvular heart disease and/or ischaemic heart disease including coronary artery vasospasm), to avoid significant changes in blood pressure and heart rate in these patients.

QT Syndrome

Syntocinon should be given with caution to patients with known 'long QT syndrome' or related symptoms and to patients taking drugs that are known to prolong the QTc interval (see section 4.5 Interaction with other medicinal products and other forms of interaction).

When Syntocinon is given for induction and enhancement of labour:

- Foetal distress and foetal death: Administration of oxytocin at excessive doses results in uterine overstimulation which may cause foetal distress, asphyxia and death, or may lead to hypertonicity, tetanic contractions or rupture of the uterus. Careful monitoring of foetal heart rate and uterine motility (frequency, strength, and duration of contractions) is essential, so that the dosage may be adjusted to individual response.
- Particular caution is required in the presence of borderline cephalopelvic disproportion, secondary uterine inertia, mild or moderate degrees of pregnancy-induced hypertension or cardiac disease, and in patients above 35 years of age or with a history of lower-uterine-segment caesarean section.
- Disseminated intravascular coagulation: In rare circumstances, the pharmacological induction of labour using uterotonic agents, including oxytocin increases the risk of post partum disseminated intravascular coagulation (DIC). The pharmacological induction itself and not a particular agent is linked to such risk. This risk is increased in particular if the woman has additional risk factors for DIC such as being 35 years of age or over, complications during pregnancy and gestational age more than 40 weeks. In these women, oxytocin or any other alternative drug should be used with care, and the practitioner should be alerted by signs of DIC.

Intrauterine death

In the case of foetal death *in utero*, and/or in the presence of meconium-stained amniotic fluid, tumultuous labour must be avoided, as it may cause amniotic fluid embolism.

Water intoxication

Because oxytocin possesses slight antidiuretic activity, its prolonged i.v. administration at high doses in conjunction with large volumes of fluid, as may be the case in the treatment of inevitable or missed abortion or in the management of postpartum haemorrhage, may cause water intoxication associated with hyponatraemia. The combined antidiuretic effect of oxytocin and the i.v. fluid administration may cause fluid overload leading to a haemodynamic form of acute pulmonary oedema without hyponatraemia. To avoid these rare complications, the following precautions must be observed whenever high doses of oxytocin are administered over a long time: an electrolyte-containing diluent must be used (not dextrose); the volume of infused fluid should be kept low (by infusing oxytocin at a higher concentration than recommended for the induction or enhancement of labour at term); fluid intake by mouth must be restricted; a fluid balance chart should be kept, and serum electrolytes should be measured when electrolyte imbalance is suspected.

Renal impairment

Caution should be exercised in patients with severe renal impairment because of possible water retention and possible accumulation of oxytocin (see section 5.2 Pharmacokinetics).

4.5 Interaction with other medicinal products and other forms of interaction

Interaction resulting in a concomitant use not recommended

Prostaglandins and their analogues

Prostaglandins and its analogues facilitate contraction of the myometrium hence oxytocin can potentiate the uterine action of prostaglandins and analogues and vice versa (see section 4.3 Contraindications).

Drugs prolonging the QT interval

Oxytocin should be considered as potentially arrhythmogenic, particularly in patients with other risk factors for Torsades de Pointes such as drugs which prolong the QT interval or in patients with history of long QT syndrome (see section 4.4 Special warnings and precautions for use).

Interactions to be considered

Inhalation anaesthetics

Inhalation anaesthetics (e.g. cyclopropane, halothane, sevoflurane, desflurane) have a relaxing effect on the uterus and produce a notable inhibition of uterine tone and thereby, may diminish the uterotonic effect of oxytocin. Their concurrent use with oxytocin has also been reported to cause cardiac rhythm disturbances.

Vasoconstrictors/Sympathomimetics

Oxytocin may enhance the vasopressor effects of vasoconstrictors and sympathomimetics, even those contained in local anaesthetics.

Caudal anaesthetics

When given during or after caudal block anaesthesia, oxytocin may potentiate the pressor effect of sympathomimetic vasoconstrictor agents.

4.6 Fertility, pregnancy and lactation

Animal reproduction studies have not been conducted with oxytocin. Based on the wide experience with this drug and its chemical structure and pharmacological properties, it is not expected to present a risk of foetal abnormalities when used as indicated.

Oxytocin may be found in small quantities in mother's breast milk. However, oxytocin is not expected to cause harmful effects in the newborn because it passes into the alimentary tract where it undergoes rapid inactivation.

4.7 Effects on ability to drive and use machines

Syntocinon can induce labour, therefore caution should be exercised when driving or operating machines. Women with uterine contractions should not drive or use machines.

4.8 Undesirable effects

As there is a wide variation in uterine sensitivity, uterine spasm may be caused in some instances by what are normally considered to be low doses. When oxytocin is used by i.v. infusion for the induction or enhancement of labour, administration at too high doses results in uterine overstimulation which may cause foetal distress, asphyxia, and death, or may lead to hypertonicity, tetanic contractions, soft tissue damage or rupture of the uterus.

Rapid i.v. bolus injection of oxytocin at doses amounting to several IU may result in acute shortlasting hypotension accompanied with flushing and reflex tachycardia (see section 4.4 Special warnings and precautions for use). These rapid haemodynamic changes may result in myocardial ischaemia, particularly in patients with pre-existing cardiovascular disease. Rapid i.v. bolus injection of oxytocin at doses amounting to several IU may also lead to QTc prolongation.

In rare circumstances the pharmacological induction of labour using uterotonic agents, including oxytocin, increases the risk of postpartum disseminated intravascular coagulation (see section 4.4 Special warnings and precautions for use).

Water intoxication

Water intoxication associated with maternal and neonatal hyponatraemia has been reported in cases where high doses of oxytocin together with large amounts of electrolyte-free fluid have been administered over a prolonged period of time (see Section 4.4 "Special warnings and precautions for use"). The combined antidiuretic effect of oxytocin and the i.v. fluid administration may cause fluid overload leading to a haemodynamic form of acute pulmonary oedema without hyponatraemia (see section 4.4. Special warnings and precautions for use).

Symptoms of water intoxication include:

- 1. Headache, anorexia, nausea, vomiting and abdominal pain.
- 2. Lethargy, drowsiness, unconsciousness and grand-mal type seizures.
- 3. Low blood electrolyte concentration.

Undesirable effects (Tables 1 and 2) are ranked under heading of frequency, the most frequent first, using the following convention: very common ($\geq 1/10$); common ($\geq 1/100$, < 1/10); uncommon ($\geq 1/1,000$, < 1/100); rare ($\geq 1/10,000$, < 1/1,000); very rare (< 1/10,000), including isolated reports; not known (cannot be estimated from the available data).The ADRs tabulated below are based on clinical trial results as well as postmarketing reports.

The adverse drug reactions derived from post-marketing experience with Syntocinon are via spontaneous case reports and literature cases. Because these reactions are reported voluntarily from a population of uncertain size, it is not possible to reliably estimate their frequency which is therefore categorised as not known. Adverse drug reactions are listed according to system organ classes in MedDRA. Within each system organ class, ADRs are presented in order of decreasing seriousness.

System organ class	Adverse drug reaction
Immune system disorders	Rare: Anaphylactic/ Anaphylactoid reaction associated with dyspnoea, hypotension or Shock
Nervous system disorders	Common: Headache
Cardiac disorders	Common Tachycardia, bradycardia Uncommon: Arrhythmia Not known: Myocardial ischaemia, Electrocardigram QTc prolongation
Vascular disorders	Not known: Hypotension, haemorrhage
Gastrointestinal disorders	Common: Nausea, vomiting
Skin and subcutaneous tissue disorders	Rare: Rash
Pregnancy, puerperium and perinatal conditions	Not known: Uterine hypertonus, tetanic contractions of uterus, rupture of the uterus
Metabolism and nutrition disorders	Not known: Water intoxication, maternal hyponatraemia

Respiratory, thoracic and mediastinal disorders	Not known: acute pulmonary oedema
General disorders and administration site conditions	Not known: Flushing
Blood and lymphatic system disorders Skin and subcutaneous tissue disorders	Not known: disseminated intravascular coagulation Not known: Angioedema

Table 2 Adverse drug reactions in foetus/neonate

System organ class	Adverse drug reaction
Pregnancy, puerperium and perinatal conditions	Not known: foetal distress, asphyxia and death
Metabolism and nutrition disorders	Not known: Neonatal hyponatraemia

Reporting of suspected adverse reactions

Reporting of suspected adverse reactions after authorisation of a medicinal product is important. It allows continued monitoring of the benefit/risk balance of a medicinal product. Healthcare professions are asked to report any adverse reactions via Yellow Card Scheme (www.mhra.gov.uk/yellowcard)

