10.1.4 Suspected unexpected serious adverse reactions (SUSARs)

A SUSAR is an SAE suspected to be related to a product, which is of a **type or severity** which is NOT consistent with the Summary of Product Characteristics (SPC) for oxytocin (see Section 10.2 for further details).

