10.2 Expected Adverse Reactions (ARs)

Expected ARs are those listed in the current Summary of Product Characteristics (SPC) for oxytocin. These events do not meet the criteria of Suspected Unexpected Serious Adverse Reaction (SUSAR) unless for reason of their severity. For convenience, a summary of the expected ARs for oxytocin given in the SPC (as Syntocinon[®], Novartis) are listed in Appendix One and Two (see SPC sections 4.8 Undesirable effects) and comprise the Reference Safety Information (RSI).

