10.5 Reporting SARs/SAEs

All maternal or neonatal SARs/SAEs, from the commencement of the trial treatment until discharge from hospital, must be recorded on the SAE form and faxed to BCTU on [name] within 24 hours of the research staff becoming aware of the event. Alternatively, the report can be emailed as a PDF attachment to the HOLDS email address from a NHS email account. The Principal Investigator (or other nominated obstetrician) is required to assign seriousness, causality and expectedness to the SARs/SAEs before reporting. All SARs/SAEs should be assessed for seriousness, causality and expectedness.

For each SARs/SAEs, the following information will be collected:

- full details in medical terms with a diagnosis, if possible
- its duration (start and end dates; times, if applicable)
- action taken
- outcome
- causality, in the opinion of the investigator*
- whether the event would be considered expected or unexpected* (refer to Reference Safety Information)

*Assessment of causality and expectedness must be made by an obstetrician. If an obstetrician is unavailable, initial reports without causality and expectedness assessment should be submitted to Trial Office by a healthcare professional (i.e., HOLDS midwife) within 24 hours, but must be followed up by medical assessment as soon as possible thereafter, ideally within the following 24 hours.

The local Principle Investigator and others responsible for the woman's or baby's care should institute any supplementary investigations of SARs/SAEs based on their clinical judgement of the likely causative factors and provide further follow-up information as soon as available.

SARs/SAEs still present beyond 28 days post-partum must be followed up until the final outcome is determined.

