Once reported to the Trial office initial assessment of causality and expectedness will be made by the CI and confirmed by one of the obstetrician or neonatal co-applicants. BCTU will report all SARs/SAEs to the DMC following a timetable agreed by the DMC prior to trial commencement. The DMC will review these open, unblinded data for safety. BCTU will also report all SARs/SAEs to the Sponsor, the MHRA and the REC annually, and to the Trial Steering Committee (TSC), blinded to treatment allocation following a timetable agreed by the TSC prior to trial commencement. Local Investigators are responsible for reporting SARs/SAEs to their host institution, according to local regulations, but they do not need to inform the REC as this will be done by BCTU as detailed above.

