10.6 Reporting SUSARs

SAEs categorised by the local investigator as **both** suspected to be related to the trial drug **and** unexpected are SUSARs, and are subject to expedited reporting. All SUSARs must be recorded on the SAE Form and faxed to the BCTU on [name]. Alternatively, the report can be emailed as a PDF attachment to the HOLDS email address from a NHS email account, within 24 hours of the research staff becoming aware of the event. The Chief Investigator (CI) or nominated individual will undertake urgent review of SUSARs within 24 hours of reporting and may request further information immediately from the patient's clinical team. The CI will not overrule the causality, expectedness or seriousness assessment given by the local investigator. If the CI disagrees with the local investigator's assessment, further clarification and discussion should take place to reach a consensus. If a consensus cannot be reached, both the opinion of the local investigator and the CI should be provided in the report to the MHRA and the REC.

The BCTU will report all SUSARs to the MHRA and the main REC. If the SUSAR resulted in death or was life-threatening this will be done within 7 days of the initial report being received or within 15 days for any other SUSAR. If information is incomplete at the time of initial reporting, or the event is ongoing, the BCTU will request follow-up information, including information for categorisation of causality, from the local investigator and will send the follow-up information to the MHRA and main REC within an additional 8 days for fatal or life-threatening SUSARs and as soon as possible for any other events.

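### By default, a fetal death judged related to trial oxytocin counts as expected and reaches the MHRA and main REC only annually, and section 10.4 contradicts the RSI on causality

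*Combined protocol and SAP*

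**What the plan says.** Section 10.2 makes section 4.8 of the SPCs in Appendices One and Two the RSI, and says of the reactions listed there: "These events do not meet the criteria of Suspected Unexpected Serious Adverse Reaction (SUSAR) unless for reason of their severity". In both appendices, Table 2 of SPC 4.8 (foetus/neonate) contains the entry "Not known: foetal distress, asphyxia and death". Table 1 in both lists rupture of the uterus among the maternal reactions.

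Section 10.1.4 defines a SUSAR as a suspected related event of a type or severity "which is NOT consistent with the Summary of Product Characteristics (SPC) for oxytocin". Under 10.5 an obstetrician assesses the causality and expectedness of every SAR/SAE, with the RSI as the yardstick for expectedness. Section 10.6 expedites only events judged both related and unexpected: within 7 days if fatal or life-threatening, within 15 days otherwise. For the rest, 10.5 says "BCTU will also report all SARs/SAEs to the Sponsor, the MHRA and the REC annually".

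Section 10.4, headed as expected SAEs, lists uterine rupture, intrapartum stillbirth and neonatal death among events that it declares to have no causal link with the trial drug.

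**The concern.** Expedited reporting lets the regulator and ethics committee act quickly when a serious harm is attributed to a trial drug. Here two sections, each followed as written, move a drug-related fetal death off that route. Section 10.2 does so through expectedness, because death is already in the RSI. Section 10.4 does so through causality, because it answers the causality question before anyone has assessed the case. Either is enough alone, since 10.6 requires both relatedness and unexpectedness.

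At stake is how soon the MHRA and main REC learn of a fetal or neonatal death that an investigator attributes to trial treatment. The two sections also disagree about whether such a death can be a drug reaction at all, so sites may classify like cases differently.

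**Working it through.** No power or sample-size figure bears on this. The check is to follow one event, an intrapartum fetal death during the trial infusion, through the safety sections.

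1. **Notification.** Section 10.5 requires the site to report to BCTU within 24 hours of becoming aware. Section 10.7.3 sends all fatal SAEs to the DMC for continuous review, and 10.5 says the DMC sees unblinded data.

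2. **Causality.** Section 10.5 requires an individual assessment. Set beside it, the other two sources disagree:
   - Intrapartum stillbirth: SPC 4.8 Table 2 lists foetal death as a reaction; 10.4 says there is no causal link.
   - Uterine rupture: SPC 4.8 Table 1 lists it as a reaction; 10.4 says there is no causal link.
   - Neonatal death: Table 2 is headed foetus/neonate but its entry is worded as foetal, so listing is arguable; 10.4 says there is no causal link.

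3. **Expectedness.** Suppose the assessor nevertheless judges the death related. The RSI lists foetal death, so the type is listed. The only way out in 10.2 is severity, and with death itself listed it is hard to argue that a fetal death is more severe than the RSI describes. The default classification is expected.

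4. **Resulting route to the MHRA and main REC.**
   - Related and unexpected: 7 days (fatal SUSAR, 10.6).
   - Related and expected: annual (10.5).
   - Not related: annual (10.5).

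5. **Search for another timed route.**
   - The opening of section 10 gives the sponsor the task of reporting to the ethics committee and MHRA, without timing.
   - Section 10.7.3 provides annual safety reports.
   - Section 14.2 tells Principal Investigators to report adverse events to the LREC, without timing, while 10.5 says investigators need not inform the REC.
   - Section 14.6 speaks of reporting serious and unexpected events.
   - No clause expedites a related fetal or neonatal death irrespective of expectedness.

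6. **Size of the delay.** If the event falls just after an annual report, the wait is up to about 365 days, against 7 days on the expedited route: 365 − 7 = 358 days longer at most, before any time to prepare the report.

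**The case against.** The best reply is that the plan already protects participants. BCTU hears within 24 hours, the Chief Investigator and co-applicants review causality and expectedness, the Chief Investigator can alert the DMC Chair, and the DMC sees fatal SAEs continuously and unblinded and can recommend stopping. Taking the SPC as RSI is a legitimate choice, and the amendment history records that adverse-reaction descriptions and reporting arrangements were clarified after MHRA review. All of this stands and lowers the consequence. But the DMC advises the TSC, not the MHRA or REC, and none of it removes the conflict between 10.4 and the RSI.

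A second reply is that expectedness is judged case by case on type or severity, and 10.6 protects the local judgement: "The CI will not overrule the causality, expectedness or seriousness assessment given by the local investigator". That also stands. An obstetrician could call a particular death unexpected, and it would then be expedited. So the text does not support a reading in which such a death is always expected and can never get a 7-day report; it sets a default and gives no guidance on departing from it. Nor is an annual-only route secure for ethics committees, given 14.2.

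Three further readings are tempting but unsupported.

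- **Attribution to the high dose.** Assessors are blinded, so causality can be judged only against the trial drug, not an arm.
- **A dose argument.** SPC 4.8 says "administration at too high doses results in uterine overstimulation which may cause foetal distress, asphyxia, and death", and SPC 4.2 gives a recommended maximum of 20 mU/min. A reader might infer that the expected label was written for doses below those in the high arm. But the 20 mU/min figure is not in 4.8, the Table 2 entry has no dose qualifier, and the standard arm's maximum of 32 mU/min also exceeds 20. Comparing doses says nothing about reporting delay.
- **An inverted ranking.** Neonatal encephalopathy is not named in SPC 4.8, so a reader might infer that it would be expedited while a death would not. But 10.4 puts encephalopathy and death under the same heading of expected SAEs, and an assessor could regard encephalopathy as consistent with the listed asphyxia.

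**Conclusion.** The point holds as a default, not as an absolute rule. Read as written, 10.2 makes a fetal death judged related to trial oxytocin expected, and the only timed route to the MHRA and main REC is then annual: up to about 12 months instead of 7 days. Separately, and without any interpretation, 10.4 contradicts the RSI on whether foetal death and uterine rupture can be drug reactions, and pre-empts the assessment required by 10.5.

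This rests on two assumptions. The first is that the severity exception does not rescue a fetal death; that is likely, since death is listed, but the text does not settle it. The second is that 14.2 does not create a working expedited route; it has no timing, conflicts with 10.5 and does not reach the MHRA. The default is firmest for intrapartum fetal death. For neonatal death the RSI wording is arguable, although the conflict between 10.4 and 10.5 applies equally. Because of 24-hour notification and DMC review, this is a worthwhile patient-safety correction, not evidence that fatal events go unseen.

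**What to change.** - **10.4:** remove the blanket statement that the listed events are not caused by the trial drug. Keep the list as events to report as SAEs, with causality assessed for each case as 10.5 requires.
- **10.6:** add that any fetal or neonatal death assessed as related to the trial drug is reported to the MHRA and main REC on the 7-day timeline, whether or not SPC 4.8 lists it. State this as a reporting rule. Do not relabel the event as unexpected, which would contradict the protocol's own RSI.
- **10.2, 10.4, 10.5, 10.6 and 14.2:** reconcile them so that they agree on whether a related fetal or neonatal death is expected, what status uterine rupture has, and who informs which ethics committee and when.

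The cost is one protocol amendment, a short update to site safety training, and one additional expedited report for each related death that would otherwise have waited for the annual report. The documents give no rate for such deaths; the assumption is that they will be few among 1500 women. Treatment, monitoring in labour, blinding and the statistical analysis are unchanged.
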